## Fear control responses:

Defensive Avoidance: Defensive avoidance will be assessed using the item format: e.g. '*I* prefer not to think about the advice given to me by the dentist' using a five point Likert scale anchored with the statements 'strongly disagree=1' and strongly agree=5'

Perceived Manipulation: Perceived manipulation will be assessed using the item format, '*The advice given to me by the dentist is untrue or manipulated*' using a five point Likert scale anchored with the statements 'strongly disagree=1' and strongly agree=5

Message Derogation: Message derogation will be assessed using the item format: '*The* advice given to me by the dentist is exaggerated' and '*I* do not personally believe the advice given to me by the dentist' using a five point Likert scale anchored with the statements 'strongly disagree=1' and strongly agree=5

Danger control response: This will be assessed using three items, with a stem 'How likely it will be before your next appointment that you will: 'follow the advice given by the dentist completely', follow some of the advice given by the dentist and; talk to someone about the advice the dentist gave you'. Responses will be in a 5 point Likert scale from 1=absolutely unlikely to 5=absolutely likely

# 6. Clinical Outcomes

i) Basic Periodontal Examination (BPE) scores (V1, V2, V3)

BPE scores are undertaken by dentists as routine in each dental check-up. Dentists will therefore, as routine, collect this data at Visit 1. They will in addition collect BPE scores at Visits 2 and 3. We will use this clinical data as a secondary outcome variable as an objectively measured indicator of behaviour change, concentrating on conversions between codes 1 (bleeding) and 0 (health).

ii) Measurement of early caries lesions using QLF (V1, V2, V3)

Formation of a 'normal' carious lesion takes at least six months (Ekanayake & Sheiham, 1987), with measurement of caries incidence using visual examination of teeth therefore only possible as a clinical outcome if follow up is extended over a significant time period. With the naked eye it is difficult to detect mineral loss in a short follow up period time because decay has to be fairly well advanced (at least 15% of mineral lost) before it can be seen by eye, usually as a white spot on the tooth. QLF extends detection of tooth mineral loss from 15% down to 0%. Thus demineralisation and remineralisation is detected in a matter of weeks. Brochner et al (2011) show significant regression of white spot lesions in four-weeks in patients where post orthodontic white spots were treated with preventive agents. Many other studies report similar findings. QLF thus provides an alternative, timely and more sensitive method for detection and measurement of early caries lesions than visual methods (De Josselin de Jong, 1995). As teeth demineralise there is a loss of fluorescence due to the increase in tooth porosity which in turn leads to a decrease in the refractive index of the carious lesion. Software allows changes in fluorescence of dental enamel to be quantified into mineral content. Detecting early caries is important because this gives an early indication of the likelihood of developing larger lesions, but at a stage where preventive behaviour can still lead to tooth remineralisation. Because QLF allows both mineral loss and gain to be quantified it is particularly useful for measuring early impacts of preventive interventions. Presence or absence of lesions will be scored on a per-surface base in each patient, using 3 photographs of buccal/labial tooth surfaces (one anterior image and right/left posterior images), producing data on percentage of surfaces affected for each patient. Data will also be recorded on severity where lesions are present, with  $\Delta Q$  denoting the product of the fluorescence loss and area over the demineralised lesion.

iii) Measurement of plaque using QLF (V1,V2,V3)

In addition to being able to quantify mineral loss and gain, QLF technology has been used to quantify regions of mature dental plaque accumulation on teeth, due to fluorescent porphyrins within bacteria which fluoresce red, with different intensities depending on the amount and maturity of plaque present related to porpyhrin concentration. Presence of red fluorescent indicates that plaque has been present for 48 hours or more, and is therefore a useful indicator of longer term tooth-brushing behaviour than that related just to the day of the oral examination. Computer based plaque analysis have been shown to be more reliable, precise, objective and sensitive (Pretty et al, 2005). Plaque Percent Index (PPI) data gathered from QLF photographs permit plaque assessment on an interval scale and shows excellent reliability when repeated measurements of the same image are analysed (Pretty et al)

al, 2005). The tooth surface area of red auto-fluorescence of dental plaque will also be measured.

## Phase 2 Analysis

# WTP

We will compare hypothetical Willingness to Pay for each of the information systems across the whole sample (primary outcome) across the 3 arms. We will also compare hypothetical WTP with WTP for a good that has been "consumed" by comparing WTP before and after receiving the information. WTP data will be analysed both descriptively, comparatively and econometrically. Descriptive data analysis will consist of WTP value means with standard deviations along with medians and quartiles for each information system. The WTP values for each system will be compared using appropriate comparative tests (e.g. most likely to be Mann Whitney U tests given the likely distribution).

In order to understand fully how the dental and demographic factors influenced values (WTP), econometric regression analyses will be carried out. A regression model of individual co-variates on WTP will be specified. The regression method will be dependent on the data but is likely to be either OLS or Tobit regression analyses. Tobit models have been recommended for analysis of WTP data because of the censoring of the data at zero (Halstead et al., 1991). The Ramsey RESET test will be used to test for model specification. Individual Tobit models will be constructed for each information system.

Finally, hypothetical WTP data for each information form will be compared to WTP following experience again using the most appropriate comparative tests.

Probable hypothesis tests to be used to compare WTP for different arms and also at different time points and econometric analysis plans to analyse factors that influence WTP. The Ramsey RESET test (Ramsey, 1969) will be used to test for model misspecification. The RESET test tests for omitted variables, incorrect functional form and correlation between independent variables and the error term. Sensitivity analysis using alternative regression analysis (e.g. tobit, OLS Interval regression analysis) will be performed to test whether the results are sensitive to model specification.

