## Procedures (see Flow diagram and Study Crib sheet)

# Visit 1 (V1):

Before their dental check-up, for patients recruited to the study a measure of the patients' literacy (REALM) will be administered by a dental nurse. The following data will then be gathered as self-reports: demographic (age, gender, income, education, employment status); psycho-graphic (previous experience of dental care, self-rated oral health, dental anxiety (MDAS); and oral health behaviours (diet, oral hygiene and smoking).

Information on patients' hypothetical incremental Willingness to Pay (WTP) for both the Traffic Light and QLF information systems (using Verbal information only as a base line for comparison), will be gathered. The systems will be explained hypothetically using written and visual information giving a generalised description of that type of information, but without reference to the patients' personal oral health status/risk. Following an outline of the 3 scenarios, patients will first be asked which of the forms of information is preferred including the current practice of Verbal information only (ranking) and then incremental WTP will be elicited for traffic light and QLF both compared to Verbal only (i.e. what extra would some be willing to pay (if at all) to receive either traffic light or QLF over verbal information only) in this face to face setting.

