WTP will be elicited using a shuffled payment card method, where a range of values are shown to the patient one at a time in a random order (Smith, 2006). The participant then decides for each value whether they are willing to pay the amount, unwilling to pay it or unsure. This then leaves a range between the lowest value that the participant is unwilling to pay and the highest value that they are willing to pay. The patient will then be asked to name the value between (and including) these values that would be the maximum they would be willing to pay. The decision for each card therefore is similar to a dichotomous choice (as recommended by Arrow and Solow, 1993)), but the whole process finishes with an open ended question. This approach minimises some of the problems associated with using either one of these methods on their own, such as starting point and range bias and making the cognitive task too difficult. Where participants give a zero value, they will be asked to identify the reason for the zero valuation from a range of options presented verbally and on a card. This will allow zeros to be later classified as true zeros or protest responses.

Baseline QLF photographs will then be taken of all patients to measure plaque levels. The patients will then brush their teeth and a second QLF photograph taken to measure tooth mineralisation. At this stage there will be no disclosure of the photograph to patients.

Patients will then have their dental check-up appointment (which will include a BPE examination). The dentist will open the randomisation envelope and patients will then be given their own personal risk information according to the randomisation schedule: either 1) Verbal only information (Model 1) or 2) Verbal information supported by a printed copy of the patients' oral health and risk of disease displayed as a traffic light (Red, Amber or Green), (Model 2) or 3) Verbal information supported by the QLF photographs taken earlier.

In the QLF arm the dentist will discuss the images with the patient in an electronic form on a Tablet PC. These patients will be offered an e mailed electronic image and/or a printed copy of the most meaningful image (either plaque or mineral loss) in a credit card size. A record will be made if an electronic image is sent. In the Traffic Light arm patients will be given a

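### The primary WTP comparison is worded both as whole-sample and as across the three arms, but hypothetical WTP is collected before allocation is disclosed, so the arm comparison should be removed and the whole-sample comparison made paired

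*Protocol*

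**What the plan says.** Under Phase 2 Analysis, WTP, the protocol states: "We will compare hypothetical Willingness to Pay for each of the information systems across the whole sample (primary outcome) across the 3 arms". The label for the primary outcome follows the mention of the whole sample, and the mention of the arms comes after it. The same section says that the values for each system will be compared, most likely with Mann-Whitney U tests. It ends with an incomplete sentence beginning "Probable hypothesis tests to be used to compare WTP for different arms and also at different time points".

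The order of events is in Procedures, Visit 1. Before the check-up, the nurse collects "hypothetical incremental Willingness to Pay (WTP) for both the Traffic Light and QLF information systems (using Verbal information only as a base line for comparison". The systems are described generically, "but without reference to the patients' personal oral health status/risk". Two sets of baseline photographs follow, and then: "Patients will then have their dental check-up appointment (which will include a BPE examination". Only then does the arm become known: "The dentist will open the randomisation envelope and patients will then be given their own personal risk information". The Randomisation section agrees that the envelope is opened by the dentist at the check-up.

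After the check-up, patients may revise their WTP for the form they experienced. The Verbal arm does not take part in this step.

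The Sample size calculation section says the size is driven by differences in WTP between the three forms of information, but expresses it as 133 in each group.

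**The concern.** Comparing forms across the whole sample sets two values from the same patient against each other, and that answers the study question. Comparing hypothetical WTP across arms sets the same quantity side by side in three groups of patients who have so far been treated alike. The null hypothesis of the second comparison is true by design. A significant result would be a chance imbalance at baseline. A non-significant one would say nothing about whether QLF is valued above Traffic Light.

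The primary sentence allows either analysis, so the primary comparison is not uniquely fixed. The risk is that a null arm comparison is reported as equal valuation of the forms, or that a chance difference is reported as an effect of the form received.

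A second problem affects the valid reading. The test named as most likely is for independent samples, but every patient supplies both values.

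**Working it through.** **The plan's own figures.** The protocol gives no effect size, SD or power for WTP, so there is no WTP calculation to reproduce. Its one calculable figure is for the plaque index, with 133 per group, SD 10, 80% power and 0.05 (taken as two-sided). The detectable difference is 10 × (1.960 + 0.842) × √(2/133) = 3.44, stated as 3.5. Power at 3.5 is 0.81. The figure holds, and it is a calculation for a contrast between arms.

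**Step 1: timing.** The order at Visit 1 is: generic descriptions, ranking and hypothetical WTP for both forms; photographs; check-up; envelope opened; personal information given; optional revision of WTP. Hypothetical WTP is complete before the arm is disclosed to anyone. Its distribution is therefore the same in all three arms, whatever patients think of QLF or Traffic Light.

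**Step 2: consequence for an arm test.** If the distribution of W given arm equals the distribution of W, the probability of rejection is the significance level for any true difference between forms. This needs no simulation, but one illustrates it.

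Assumptions, since the protocol gives none:
- 400 patients, split 134/133/133.
- Latent WTP normal with SD 1, mean 0.5 for Traffic Light and 0.5 + d for QLF, censored at zero.
- Within-patient correlation ρ of 0.5 or 0.8.
- 2,000 simulated trials per setting.

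| d (SD) | ρ | Three-arm Kruskal-Wallis on QLF WTP | Paired signed-rank, n = 400 | Mann-Whitney U, both values of all 400, pairing ignored |
|---|---|---|---|---|
| 0 | 0.5 | 0.046 | 0.053 | 0.0095 |
| 0 | 0.8 | 0.055 | 0.048 | 0.0005 |
| 0.2 | 0.5 | 0.055 | 0.943 | 0.825 |
| 0.2 | 0.8 | 0.052 | 1.00 | 0.932 |
| 0.35 | 0.5 | 0.051 | 1.00 | 1.00 |
| 0.35 | 0.8 | 0.052 | 1.00 | 1.00 |
| 0.5 | 0.5 | 0.052 | 1.00 | 1.00 |
| 0.5 | 0.8 | 0.053 | 1.00 | 1.00 |

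The arm test stays at about 0.05 in every row.

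**Step 3: what the whole-sample comparison can detect.** By normal approximation at 80% power, the detectable difference between two values from the same 400 patients is 2.80 × √(2(1 − ρ)/400). This gives 0.17 SD at ρ = 0.3, 0.14 SD at 0.5 and 0.09 SD at 0.8. For two independent groups of 133 it is 2.80 × √(2/133) = 0.34 SD.

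**Step 4: why Mann-Whitney U does not fit.** It treats the 400 pairs as 800 independent values, so it overstates the variance of the contrast when ρ is positive. As a rough guide, the critical value of 1.96 acts like 1.96/√(1 − ρ). That is 2.34 at ρ = 0.3 (two-sided error 0.019), 2.77 at 0.5 (0.006) and 4.38 at 0.8 (below 0.001). Simulation agrees, with type I error of about 0 to 3% for ρ from 0.3 to 0.8. At 0.2 SD and ρ = 0.5, ignoring the pairing lowers power from 0.94 to 0.82.

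**The case against.** The strongest reply is that the protocol already plans the right comparison. The primary label sits next to the whole sample. The objectives, the sample size section, the descriptive statistics and the Tobit models are all organised by form of information. On that reading, the reference to three arms may only mean that patients are pooled over them. This stands in large part. A reader might infer that the primary analysis is an arm comparison and cannot show which form is valued, but the protocol does not support that. The data are sound and a valid comparison is named. What remains is that the sentence also names the arms, and that part is uninformative if carried out as worded.

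Four narrower points:
- A reader might take "Probable hypothesis tests to be used to compare WTP for different arms" as a plan to test hypothetical WTP by arm. The sentence does not mention hypothetical WTP, and comparing revised WTP between the Traffic Light and QLF arms after the check-up would be legitimate.
- Testing both values between every pair of arms, six tests in all, would give at least one false arm difference in roughly 18 to 23% of trials under assumed distributions. The protocol specifies no such family, so this is not the size of the problem.
- A looser reading compares QLF WTP in the QLF arm with Traffic Light WTP in the Traffic Light arm. That does carry information, but its simulated power at 0.2 SD is only 0.32 to 0.33. It uses two arms rather than three and discards most of the values.
- The Randomisation section has a nurse randomise after recruitment, so assignment may precede the WTP questions. The accurate description is therefore before disclosure of allocation. The envelope stays closed until the check-up, so the conclusion is unchanged.

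**Conclusion.** The primary WTP comparison is stated in contradictory terms. One of its two readings, hypothetical WTP compared between arms, has power equal to alpha whatever patients prefer: about 5% for a single three-arm test. That follows from the timing at Visit 1 and does not depend on the assumed distributions. The other reading, a comparison of forms over the whole sample, is valid and can be done with the planned data, so the primary outcome is not lost.

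The whole-sample comparison needs a paired test. The figures for this (power of at least 0.94 at 0.2 SD for ρ of 0.5 or 0.8, and Mann-Whitney type I error of about 0 to 3% for ρ of 0.3 to 0.8) rest on assumed distributions and correlations. The error from ignoring the pairing is on the conservative side when ρ is positive. Because this concerns the definition of the primary analysis, it should be settled before the data are analysed.

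**What to change.** In Phase 2 Analysis, WTP:

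1. Remove the reference to the three arms from the primary sentence.
2. Define the primary comparison as QLF against Traffic Light incremental WTP within patients, pooled over all 400 irrespective of allocation. Each incremental value is already the contrast with Verbal.
3. Replace Mann-Whitney U with a paired method for this comparison, for example the Wilcoxon signed-rank test.
4. Show hypothetical WTP by arm as a baseline description only, without tests.
5. Complete the unfinished sentence on tests by arm, and limit it to WTP given after the check-up in the Traffic Light and QLF arms.
6. State that the primary result will be reported as a within-patient contrast, not a randomised one.

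The cost is a rewording of one section. No data, visits or patients are added.

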### Phase 2: Experimental study in four dental practices

The quantitative study will help us to address final four objectives:

- To measure individuals' preferences, by using the economic preference based valuation methodology WTP for the three different methods of giving information.
- To identify differences in preference for different types of information by differing demographic, behavioural and psychographic groups.

- To use variables from derived established models of the behavioural change process to predict the likelihood that different forms of communication will lead to behaviour change; and to measure any actual behaviour change and link these with differences in valuations.
- To conduct a cost-benefit framework analysis of the three different methods and to explore financial implications for NHS dentistry.

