## Sample size calculation

As the primary outcome in this study is willingness to pay (WTP), this has been used to calculate the sample size. Differences in mean and median WTP values between the three forms of information are therefore the primary driver of sample size. Lancsar & Louviere (2008) highlight the complexities and problems of performing sample size calculations for stated preference surveys such as discrete choice experiments and contingent valuation studies (Lancsar & Louviere, 2008). In particular, the parameters that will be estimated by the CV survey (willingness to pay) must be known in advance in order to conduct a useful sample size calculation – information we do not have in advance of conducting this work. Previous studies however, using CV in health care settings have included samples ranging from less than 50 to over 1000 respondents. Recent CV work in dentistry has also used similar sizes (between 36 and 200 per group), albeit looking at treatments rather than provision of information (Rosvall et al., 2009). So, we believe that a sample size of 400 i.e. 133 in each group will be adequate in this case.

Whilst WTP is the primary outcome measure, and sample size calculation was done on this basis, we have however calculated the implications of this sample size for the detection of secondary (clinical) outcome effects. Thus we have also carried out a sample size calculation using the secondary outcome of plaque percent index (PPI), (measured using QLF). Published data on a group of 38 college students showed a mean PPI of 14.8, with a standard deviation of 7.7 (Aleksejuniene et al., 2006). As this is likely to be a more homogeneous population than in this study, we can use a more conservative estimate of s.d. of 10, to calculate that a sample size of 133 per group would allow us to detect a mean difference of 3.5 in PPI between groups, with 80% power, at the 0.05 significance level.

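### The primary willingness-to-pay comparison is within-patient, but the only test the protocol names for it assumes independent samples, and the same sentence also describes it as a comparison of three arms

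*Protocol*

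**What the plan says.** The Sample size calculation section makes WTP the primary outcome and the contrast between forms its target: "Differences in mean and median WTP values between the three forms of information are therefore the primary driver of sample size". It gives no assumed WTP difference or SD, and it justifies 400 patients as 133 per group.

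Under Procedures, Visit 1, each recruited patient supplies "Information on patients' hypothetical incremental Willingness to Pay (WTP) for both the Traffic Light and QLF information systems". The patient first ranks the three forms, and then "incremental WTP will be elicited for traffic light and QLF both compared to Verbal only". This happens face to face before the check-up. Later in the same visit the dentist opens the envelope and the patient receives the allocated form of information. Zero answers are followed up so that they can be classed as true zeros or protest responses.

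Phase 2 Analysis, WTP, states the primary comparison as follows: "We will compare hypothetical Willingness to Pay for each of the information systems across the whole sample (primary outcome) across the 3 arms". The values for each system are then to be "compared using appropriate comparative tests (e.g. most likely to be Mann Whitney U tests given the likely distribution". For regression, "Individual Tobit models will be constructed for each information system". The before-and-after-experience comparison is left to whichever test is most appropriate. No paired test is named for WTP anywhere in the protocol.

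**The concern.** Two values from the same person in the same sitting are not independent. Someone with more money, or more interest in their teeth, will tend to give higher figures for both forms. The stated reason for Mann-Whitney is the shape of the distribution. Skew does argue for a rank method, but with paired data that means a paired rank method. An independent-samples test ignores the within-patient correlation and misstates the precision of the primary contrast.

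The second difficulty is the reference to three arms. Hypothetical WTP is given before the patient knows the allocation, so the arms can differ on it only by chance. Verbal is the reference for the increments and has no WTP of its own, so there is no third value to compare. A reader cannot tell from the sentence which comparison is primary. At stake are power and correct inference on the primary outcome, and a risk that a baseline check is reported as the main result.

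**Working it through.** **The protocol's own figure.** There is none for WTP. The only computed figure is for the secondary plaque index: 133 per group, difference 3.5, SD 10, two-sided 0.05 (sidedness assumed). Power = Φ(3.5 / (10·√(2/133)) − 1.96) = Φ(2.854 − 1.96) = Φ(0.894) = 81%, against 80% stated. That figure reproduces but does not bear on WTP.

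**Inputs for WTP.** n = 400 pairs (Participants; Visit 1), nominal α = 0.05. The correlation ρ between a patient's two answers and the size of the difference are not in the protocol. I take ρ = 0.3 to 0.7 and a shift of 0.15 SD as assumptions.

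**Size of an unpaired test on paired data.** The true variance of the difference in means is 2σ²(1 − ρ)/n, while the unpaired test assumes 2σ²/n. Its standard error is too large by the factor 1/√(1 − ρ), so the actual type I error is about 2·[1 − Φ(1.96/√(1 − ρ))]:

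- ρ = 0.3: 1.96/0.837 = 2.34, giving 1.9%
- ρ = 0.5: 1.96/0.707 = 2.77, giving 0.56%
- ρ = 0.7: 1.96/0.548 = 3.58, giving 0.03%

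**Simulation.** 400 pairs, right-skewed rounded values with about 30% zeros, ρ and the shift set on the underlying normal scale; 3,000 replicates under the null and 1,500 under the shift.

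| ρ | Type I error, Mann-Whitney | Type I error, signed-rank | Power at 0.15 SD, Mann-Whitney | Power at 0.15 SD, signed-rank |
|---|---|---|---|---|
| 0.3 | 2.3% | 5.0% | 54% | 65% |
| 0.5 | 0.6% | 4.7% | 54% | 77% |
| 0.7 | 0.03% | 4.8% | 52% | 93% |

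**Larger effects.** By normal approximation, unpaired power is Φ((δ/√(2/400) − 1.96)/√(1 − ρ)) and paired power is Φ(δ/√(2(1 − ρ)/400) − 1.96). At δ = 0.20 SD and ρ = 0.5 these are Φ((2.83 − 1.96)/0.707) = 89% and Φ(4.00 − 1.96) = 98%. At δ = 0.25 SD they are Φ((3.54 − 1.96)/0.707) = 99% and Φ(5.00 − 1.96) = 99.9%. The formula assumes normal data, and the skewed, zero-heavy simulation gives somewhat lower power.

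**Detectable difference at 80% power.** Paired, (1.96 + 0.842)·√(2(1 − ρ)/400): 0.17, 0.14 and 0.11 SD for ρ = 0.3, 0.5 and 0.7. Unpaired test on the same 400 patients, 1.96·√(2/400) + 0.842·√(2(1 − ρ)/400): 0.19, 0.18 and 0.17 SD. Two independent groups of 133, which is how the sample size section frames it: 2.802·√(2/133) = 0.34 SD.

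**Arm comparison.** With 133 against 133 and values given before allocation is revealed, the null holds by construction. Simulated rejection was 5.1%, which is the nominal error rate and nothing more.

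**The case against.** The protocol does not commit itself. Mann-Whitney is offered as a likely example among appropriate tests, and a SAP may name something else. That stands: a reader might infer that the trial will certainly be analysed this way, and the text does not say so. It is nevertheless the only test named for the primary outcome, and its stated reason is distribution alone.

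The mention of arms may be loose wording for forms of information, since the same sentence says whole sample and the sample size section speaks of forms. That is plausible, and it is why this part is a request for clarity. It does not show that a baseline comparison is the intended primary result.

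Mann-Whitney is also legitimate somewhere in this trial. After the check-up, patients revise their value only for the form they experienced, so comparing revised WTP between the Traffic Light and QLF arms is a comparison of independent patients.

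Four further criticisms are tempting and are not supported:

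- The per-form Tobit models do not repeat the error. Each uses one value per patient, and their stated purpose is to describe what influences the values. Nothing says that they alone test the objective "To identify differences in preference for different types of information by differing demographic, behavioural and psychographic groups", and a direct preference ranking is collected as well.
- No wrong test is named for the before-and-after comparison.
- That Mann-Whitney targets neither a mean nor a median is no argument for signed-rank, which does not do so either when differences are skewed. Means and medians are to be reported in any case.
- It would be too strong to say that WTP precedes randomisation. The nurse handles randomisation after recruitment. What clearly comes later is the opening of the envelope.

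**Conclusion.** The point holds in a limited form. The primary contrast between forms is paired by design, the one test named for it is for independent samples, and the reference to three arms has no effect to estimate for hypothetical WTP.

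A reader might fear false positive findings. With positively correlated answers the opposite happens: type I error falls below 5%, the inference is too cautious, and point estimates are unaffected. Under the assumed ρ of 0.3 to 0.7 the cost at a 0.15 SD shift is 11 to 41 percentage points of power (65 − 54 and 93 − 52). At 0.25 SD it is slight. These sizes rest on an assumed correlation, share of zeros and effect. The mismatch between design and named test does not. Negative correlation would reverse the direction, but nothing in the protocol suggests it.

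**What to change.** In Phase 2 Analysis, WTP:

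- State the primary contrast as D = WTP(QLF) − WTP(Traffic Light) within each patient, in all patients with valid valuations. State a rule for protest zeros, using the classification already planned at Visit 1.
- Report the mean of D with a bootstrap confidence interval, plus a Wilcoxon signed-rank test.
- Report each form's mean incremental WTP over Verbal with a confidence interval.
- Delete the reference to three arms for hypothetical WTP.
- Keep Mann-Whitney only for comparing post-experience WTP between the Traffic Light and QLF arms.

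The per-form Tobit models can stay as planned. Regressing D on the covariates would be a useful optional addition for the objective on preference differences between groups, but it corrects no error.

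The cost is a change of wording in the protocol, carried into the SAP if there is one. No new data, visits or patients are needed.
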